Lingual Endurance Exercise in Treating Post-Stroke Dysphagia NCT05523973

Last Institutional Review Board Approval Date: 2/18/25

Study Protocol

All procedures and study team members were approved by University of Cincinnati Institutional Review Board (IRB# 2022-0218). A convenience sample of participants were recruited from word-of-mouth referrals (e.g. UC stroke team) and information flyers that were distributed locally throughout the community and at other institutions in the area. Participants were eligible to participate if they had a history of ischemic stroke, were 21 years of age or older, at least 3 months since initial ischemic stroke, and able to follow 2 step directions. Exclusion included any history of dysphagia prior to the ischemic stroke, if participant was pregnant, or had a history of temporomandibular joint disorders. Final eligibility for full protocol enrollment included at least one impaired oral component score according to the MBSImP (Modified Barium Swallow Impairment Profile). This was judged at time of initial visit in the fluoroscopy suite by an MBSImP trained speech language pathologist (SLP).

Study Visits

This study used a prospective quasi-experimental design, with pre-test and post-test measures. Study visits included an initial in-person baseline visit with patient reported outcome measures (Swallowing Quality of Life Questionnaire, SWAL-QoL, and Eating Assessment Tool, EAT-10) and a modified barium swallow study (MBSS) followed by 8-10 weeks of at home lingual exercise with use of the TongueometerTM device. Weekly virtual visits completed with a license speech language pathologist. At the end of the 8-10 weeks participants came for an in person visit for post-treatment data collection. Participants were asked to complete lingual presses based on 75% repetitions at 50% of their maximum isotonic press. Participants were assigned to complete this task 3 times per day. Half of the participants were instructed to complete this task 2 times a day and once a day to do 10 effortful swallows with feedback from the device. Post-treatment data were collected at a final study visit where the same PROs were administered (SWAL-QoL, EAT-10) along with a post-treatment MBSS. Procedural details for study visits and exercises described below:

Modified Barium Swallow Study

A standard MBSImP protocol was utilized under videofluoroscopy using Varibar Barium products (Varibar® E-Z-EM, Inc. 40% w/v ratio. This includes 12 bolus trials including: thin (International Dysphagia Diet Standardization Initiative, IDDSI 0), mildly thick (IDDSI 2), moderately thick (IDDSI 3), and Varibar pudding (IDDSI 4+), and a solid (cookie) with 5ml Varibar pudding.

Lingual Pressure Measures

Two lingual manometers were used for data collection at the pretreatment and post treatment visits. Collected with the Iowa Oral Performance Instrument (IOPI), the following measures were recorded (in repetitions, time, or kP) in the anterior position: swallow pressure x3 (saliva swallow), effortful swallow x3 (swallow with focus on muscle contraction and tongue pressing to the roof of the mouth), maximum isotonic pressure (MIP) x3 (press as hard as able and release), isometric endurance (ISO-M) x1 (press and hold at 50% of the highest MIP). Posterior lingual measures with IOPI were measured: MIP x3, ISOM, isotonic endurance maximum (ISO-T) (press and release as many times until fatigued to reach 50% of posterior MIP). The TongueometerTM device, was sent home with the participants for their at home exercise. To determine lingual exercise, baseline TongueometerTM measurement included anterior ISO-T. Participant were prescribed 75% anterior lingual presses at 50% of

their max MIP. For example: if patients' max MIP was 50 kPa and max ISO-T was 100 presses. Participant would be asked to complete 75 presses with force at least 25 kPa.

Adherence Monitoring

TongueometerTM device allows for virtual reports of adherence data and exercise parameters (pressure settings) to be sent securely to study team. Participants met with SLP virtually every week. Every two weeks participants Max MIP x3 and new ISO-T was measured updated number or repetitions, and max press was provided.

MBSS Data Analysis

Each pre and post MBS was rated by two license speech language pathologist for MBSImP, , and pixel based and timing measures following the Analysis of Swallowing Events, Physiology, and Timing (ASPEKT) method. If discrepancies were noted, they were resolved during consensus meetings.

Statistical analysis

Descriptive statistics were calculated on all variables. Frequencies and percentages are reported for categorical variables. The normality of continuous variable distributions were assessed using histograms and box plots. For normally distributed continuous variables, means and standard deviations are reported, while . medians and interquartile ranges are provided for non-normally distributed continuous variables.

To examine treatment effects, differences in baseline measures from pre-treatment to post treatment were calculated, including EAT-10 scores; IOPI measures: average swallow pressure (kPa) over 3 trials, maximum effortful pressure (kPa) over 3 trials, maximum anterior max strength (kPa) over 3 trials, anterior isometric endurance max (seconds), and maximum anterior isotonic endurance (reps); maximum posterior strength (kPa) over 3 trials, posterior isometric endurance max (seconds), posterior isotonic endurance max (reps); MBSImP Oral Total scores, MBSImP Pharyngeal Total scores; and Swallowing Quality of Life questionnaire scores (SWAL-QOL), including overall total score, eating duration, food selection, fear, and fatigue; and ASPEKT measures, including Swallow reaction time, Pharyngeal swallow duration, UES opening, Laryngeal vestibular closure reaction time, Laryngeal vestibular closure duration, Preswallow residue, Vallecular residue, Pyriform sinus residue, Other residue, Pharyngeal area at max constriction, Maximum opening of UES, and Peak hyoid movement.

Linear regression models were used to examine differences in baseline measures from pretreatment to post treatment. Treatment group (Endurance only vs Endurance plus transference) and baseline measures were included as covariates. Models were evaluated for parsimony. Treatment group effects that were not statistically significant were eliminated from the model and re-evaluated. Residuals were examined to assess model fit. Bowker's test of symmetry was used to test for differences in PAS score category and FOIS from pre- to post-treatment. Cohen's d was used to calculate effect sizes. Statistical significance was determined at p-values less than 0.05. All analyses were conducted using SAS version 9.4 (SAS Institute, Cary, NC).

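### The 3-month entry interval runs from the initial stroke, so a participant with a recent recurrence could qualify and natural recovery could enter the pre-to-post change

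*Combined protocol and SAP*

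**What the plan says.** All entry criteria stand in the opening paragraph under Study Protocol.

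- Stroke history: "Participants were eligible to participate if they had a history of ischemic stroke". This is not limited to a first or single stroke.
- Timing: "at least 3 months since initial ischemic stroke".
- Exclusions: "Exclusion included any history of dysphagia prior to the ischemic stroke, if participant was pregnant, or had a history of temporomandibular joint disorders".
- Last step: "Final eligibility for full protocol enrollment included at least one impaired oral component score according to the MBSImP", judged at the initial fluoroscopy visit.

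Under Study Visits, the design is given as follows: "This study used a prospective quasi-experimental design, with pre-test and post-test measures". Baseline is "followed by 8-10 weeks of at home lingual exercise" and then the post-treatment visit. Both programmes exercise; half of the participants replace one of the three daily sessions with effortful swallows.

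The Statistical analysis section begins its inferential part with "To examine treatment effects, differences in baseline measures", taken from before to after treatment. The regression models include programme and baseline measures. The programme term is removed when it is not significant. Time since stroke is not named as a covariate.

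**The concern.** In a study without an untreated group, a minimum interval since stroke is the entry rule that keeps early natural recovery out of the measured change. Here it is tied to the initial event. For a person with one stroke that makes no difference. For a person with two, the interval can be satisfied by the first while the second, which may be the one that caused the dysphagia, is only weeks old.

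Recovery in such a person would add to the mean change on any outcome that improves naturally. The analysis has nothing to separate it from a response to exercise. The contrast between the two programmes would be affected only if such people were unevenly spread between them. That is possible, since no randomization is described, but the documents give no way to size it.

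**Working it through.** **Does the text admit the case?** Take a person with a first ischemic stroke years ago and no dysphagia after it, then a second stroke two weeks ago with new dysphagia.

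1. History of ischemic stroke: met.
2. Three months since the initial stroke: met, by the first stroke.
3. Prior-dysphagia exclusion: not triggered, whichever stroke it refers to, because there was no dysphagia before either one.
4. Pregnancy and temporomandibular joint exclusions: not relevant.
5. An impaired oral component at baseline: plausible, given new dysphagia.

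The person qualifies. No stated criterion asks for the latest stroke date or for stable swallowing.

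**How large could the effect be?** The documents give no sample size, SD, correlation or share of recurrent cases, so there is no plan figure to reproduce. The inputs below are all assumptions:

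- n = 20
- pre-post correlation 0.7
- share with a recent recurrence f = 10%-25%
- natural recovery in those people r = 0.5-1.0 baseline SD
- no true effect of exercise
- two-sided test at 0.05 (the plan gives 0.05 without saying one- or two-sided)

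A one-sample t-test on change stands in for the regression.

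Formulas, in baseline SD units:

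- Shift in mean change = f × r.
- Variance of change without recovery = 2(1 − 0.7) = 0.6, so SD = 0.775.
- Variance added because only some people recover = f(1 − f)r².
- Standardized shift d = f·r / √(0.6 + f(1 − f)r²).
- Rejection rate from the noncentral t with 19 degrees of freedom and noncentrality d√20.

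| f | r | shift | SD of change | d | rejection, noncentral t | rejection, simulated with exactly f × 20 people recovering |
|---|---|---|---|---|---|---|
| 10% (2 of 20) | 0.5 | 0.05 | √0.6225 = 0.789 | 0.063 | 0.058 | 0.054 |
| 10% (2 of 20) | 1.0 | 0.10 | √0.69 = 0.831 | 0.120 | 0.081 | 0.065 |
| 25% (5 of 20) | 0.5 | 0.125 | √0.6469 = 0.804 | 0.155 | 0.101 | 0.092 |
| 25% (5 of 20) | 1.0 | 0.25 | √0.7875 = 0.887 | 0.282 | 0.224 | 0.190 |

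The range is therefore about 5%-22% per outcome. With one person in 20, simulation at either recovery size gives about 0.050. With none, the shift is zero.

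The added variance matters at the top of the range. Leaving it out gives d = 0.25/0.775 = 0.323 and a rejection rate of 0.278, which is too high because it treats everyone as shifting by the same amount.

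**The case against.** Four points can be made against this.

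- **The term may mean the qualifying stroke.** The eligibility text speaks of the stroke in the singular throughout, and *initial* may have been intended as the onset event that brought the person into the study. That may be so, but the document does not define it, and for someone with two strokes the plain meaning is the first. The exclusion "Exclusion included any history of dysphagia prior to the ischemic stroke" has the same ambiguity.
- **The affected group is narrow.** It needs an earlier stroke, a second one under 3 months ago and an impaired oral score. If the exclusion refers to the latest stroke, it also removes anyone with dysphagia left from an earlier one. This stands as a limit on size. It does not catch people whose dysphagia began with the recurrence, who are the ones likely to be still recovering.
- **The main cause is the missing untreated control.** This is correct. Recovery cannot be ruled out for any participant, and the entry clock only adds to that.
- **The study may have finished recruiting.** The document is written in the past tense. If so, rewording the criterion changes nothing, but the latest stroke dates and a sensitivity analysis remain useful.

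A reader might infer that natural recovery has in fact been counted as response to exercise, or that the reported changes are unreliable for this reason. The documents do not support that: nowhere do they say that anyone with a recent recurrence took part.

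**Conclusion.** The gap in the rule is real; its effect on this study is unknown and may be zero. The criterion as worded can admit a person in early recovery from a second stroke, and the analysis would attribute that recovery to treatment. Under the assumed 20 participants, correlation of 0.7, 10%-25% share and 0.5-1.0 SD recovery, the bias is 0.05-0.25 baseline SD and the false-positive rate per outcome about 5%-22%. The upper end needs five of 20 participants with a recent recurrence, a share for which the documents offer no evidence. The point is worth correcting because the correction is cheap and the data to settle it should be easy to obtain.

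**What to change.** 1. State that the 3-month interval is counted from the most recent stroke.
2. Name the stroke to which the prior-dysphagia exclusion refers.
3. Record and report each participant's most recent stroke date.
4. For those already enrolled, rerun the change analyses without anyone less than 3 months from their latest stroke at baseline. If there is no such person, one sentence saying so closes the point.

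The cost is two clauses in the eligibility paragraph, one date field and one sensitivity analysis. If recruitment continues, a few people with recurrent stroke enter later; if it is over, the sensitivity analysis may lose a few participants. Items 3 and 4 can be done in either case. None of this replaces an untreated control, so the results should still be described as pre-to-post change.

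### The swallow study that decides entry also supplies the baseline Oral Total, so part of its pre-post improvement can be regression to the mean, of a size the documents do not determine

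*Combined protocol and SAP*

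**What the plan says.** - **Entry (Study Protocol).** "Final eligibility for full protocol enrollment included at least one impaired oral component score according to the MBSImP". One trained speech language pathologist makes this judgement in the fluoroscopy suite at the first visit. The section does not say what score counts as impaired.
- **Baseline imaging (Study Visits).** The baseline visit has questionnaires "and a modified barium swallow study (MBSS) followed by 8-10 weeks of at home lingual exercise with use of the TongueometerTM device". No separate screening study, run-in or repeat baseline is described.
- **Design (Study Visits).** "This study used a prospective quasi-experimental design, with pre-test and post-test measures". All participants do lingual exercise; the groups differ in one daily session: "Half of the participants were instructed to complete this task 2 times a day and once a day to do 10 effortful swallows". There is no untreated group.
- **Scoring (MBSS Data Analysis).** "Each pre and post MBS was rated by two license speech language pathologist for MBSImP", with disagreements settled by consensus.
- **Analysis (Statistical analysis).** "To examine treatment effects, differences in baseline measures from pre-treatment to post treatment were calculated", and the list includes "MBSImP Oral Total scores, MBSImP Pharyngeal Total scores". The regressions adjust for group and baseline, a non-significant group term is dropped, and Cohen's d is the effect size.

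**The concern.** Admission depends on how the oral phase looked on one day, and the score from that same study is then the pre-treatment value of Oral Total. Among people near the boundary, those having a worse day are admitted and those having a better day are not. On average, therefore, the baseline error of the admitted group leans towards impairment. A second study carries no such lean, so the mean is expected to improve (taken here as a fall in score) even if the exercise does nothing.

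With no untreated group and no second baseline, the pre-post test cannot separate this shift from a treatment effect. Dropping a non-significant group term leaves the overall change as the main result. Oral Total is also the outcome scale on which people were selected, so the bias is most direct there.

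**Working it through.** **Inputs.** The documents give no sample size, SD, test-retest correlation or share of screened people who pass, so there is no figure of the plan's to reproduce. Everything below is an illustration under assumptions: *p* is the share admitted on the oral criterion, *r* the test-retest correlation, *n* the number analysed, and the test is two-sided at 0.05.

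**Step 1: expected change with no treatment effect.** Let the score be approximately normal with SD 1 among all screened, and let people be admitted above a cut-off *c* = z(1 − p). Their mean first score is φ(c)/p. Their expected second score is r × φ(c)/p. The difference is

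spurious improvement = (1 − r) × φ(c)/p.

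For p = 0.50, φ(c)/p = 0.798; then 0.2 × 0.798 = 0.16 and 0.4 × 0.798 = 0.32. For p = 0.90, φ(c)/p = 0.195; then 0.2 × 0.195 = 0.04 and 0.4 × 0.195 = 0.08.

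In SD of all persons screened:

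| Share admitted | φ(c)/p | r = 0.9 | r = 0.8 | r = 0.6 |
|---|---|---|---|---|
| 50% | 0.798 | 0.08 | 0.16 | 0.32 |
| 70% | 0.497 | 0.05 | 0.10 | 0.20 |
| 80% | 0.350 | 0.035 | 0.07 | 0.14 |
| 90% | 0.195 | 0.02 | 0.04 | 0.08 |
| 99% | 0.027 | 0.003 | 0.005 | 0.01 |

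**Step 2: separate readings.** The entry judgement and the consensus score are different readings of one study. If they share only a fraction *s* of the error, the result becomes s × (1 − r) × φ(c)/p. With s = 0.5, r = 0.6 and p = 0.50 this is 0.5 × 0.4 × 0.798 = 0.16 instead of 0.32. Only with s = 0 does it vanish. Variation between boluses and between days belongs to the study itself and stays shared however many people read it.

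**Step 3: baseline covariate.** In a regression of change on centred baseline, the intercept equals the mean change. The covariate narrows the residual but leaves the shift in place.

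**Step 4: simulation with zero true change** (2,000 replicates per setting, n = 40 assumed, all error shared unless stated). Rejection rates:

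| Setting | Paired test | Baseline-adjusted intercept |
|---|---|---|
| 50% admitted, r = 0.6 | 67% | 70% |
| 50% admitted, r = 0.8 | 36% | 37% |
| 70% admitted, r = 0.6 | 29% | 33% |
| 70% admitted, r = 0.8 | 17% | 18% |
| 90% admitted, r = 0.6 | 9% | 12% |
| 90% admitted, r = 0.8 | 7% | 8% |
| 50% admitted, r = 0.6, half the error shared | 21% | 27% |

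With no shared error the mean change is within ±0.011 SD, the paired test rejects in about 4 to 6%, and the adjusted intercept in about 6 to 10%. The small excess of the adjusted test is therefore not due to selection. The between-group test stays at 3.5 to 6.6% in every setting.

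**Step 5: Cohen's d.** The plan does not state its denominator. As mean change over SD of change, the simulated spurious d at n = 40 is 0.39 (50% admitted, r = 0.6), 0.26 (50%, r = 0.8), and 0.09 and 0.07 (90%, r = 0.6 and 0.8).

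**The case against.** **The entry bar is low.** A reader might infer that only unfavourable chance variation gets a person into the study. The documents do not support that: one impaired component suffices, so someone with several passes on a good day too. Chance decides only near the boundary. If almost everyone screened passes, the bias is negligible (about 0.01 SD or less at 99%). This stands, and it is why the admitted share must be reported.

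**The model is not the criterion.** The rule acts on any one component, whereas the formula cuts a normal total score. In simulations of a floor-limited sum of components (structure assumed), with any non-zero score counting as impaired and 50 to 80% admitted, the bias was about 0.6 to 0.8 of the formula. With a stricter definition (2 or more) and about 40% passing, the formula was about right; at lower pass rates it understated the bias. A reader might also restate the bias in SDs of the admitted group, using the truncated-normal value of 0.60 at 50% admitted. That is not supportable: the same floor-limited model, with any non-zero score counting, gave an admitted SD of about 0.86 to 1.09 of the screened SD. The sizes above are therefore only indicative.

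**Two-rater consensus.** It separates much of the rater error from entry, but not the variation of the swallow itself. It reduces the bias without removing it.

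**Scope.** Oral Total is one of 28 measures listed for pre-post differences (EAT-10 1, anterior IOPI 5, posterior IOPI 3, MBSImP 2, SWAL-QOL 5, ASPEKT 12), and none is named primary. The uncontrolled design is openly declared. Both are true; they limit the reach of the point but do not answer it for Oral Total.

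**Same study?** The documents do not say outright that the entry study is the rated pre-treatment study. It is an inference, but no other pre-treatment study is described.

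**Conclusion.** The point holds for the within-person change in Oral Total and its Cohen's d. The direction is known (towards improvement) and nothing in the plan removes it. The size is not known: it rests on the share admitted, the test-retest correlation, the error shared between the entry reading and the consensus score, and the undefined meaning of impaired. The plausible span runs from trivial to enough to produce a significant result alone.

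A reader might go further and conclude that any Oral Total improvement is an artefact, or that the comparison of the two exercise groups is biased. Neither follows. Regression to the mean can account for part of a change of unknown size, and the group contrast is unaffected if both groups were selected alike. Other outcomes are affected only as far as their baseline error correlates with the oral score. This limits the reading of one outcome and does not invalidate the study.

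**What to change.** 1. Report how many people had the baseline swallow study and how many were admitted on the oral criterion, and state what score counted as impaired. The counts alone may show that the issue is trivial.
2. Beside the Oral Total change, give a sensitivity analysis of the change expected from regression to the mean at the observed admitted share, over a stated range of test-retest correlation (for example 0.6 to 0.9). Under the simple model that range is 0.02 to 0.08 SD at 90% admitted and 0.08 to 0.32 SD at 50%.
3. Use the baseline scores of screen failures for the screened SD only if those recordings were kept and may be scored; the documents do not say so. Otherwise let the admitted group's SD stand in, and state that as an assumption.
4. Do not interpret an Oral Total change within that range as a treatment effect.
5. Rest the main pre-post claim on outcomes not used for selection, such as the IOPI measures, EAT-10 and SWAL-QOL. This deals with the selection bias only; those outcomes still lack an untreated comparison.

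The cost is a screening count, one short calculation and a less favourable Oral Total result. No new participants or visits are needed.

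### Does the absence of anterior isotonic endurance from the IOPI measurement list undermine its analysis as an IOPI outcome?

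*Combined protocol and SAP*

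**What the plan says.** The Lingual Pressure Measures section opens with "Two lingual manometers were used for data collection at the pretreatment and post treatment visits". For the IOPI it then says that "the following measures were recorded (in repetitions, time, or kP) in the anterior position", and lists four items: saliva-swallow pressure, effortful swallow, maximum pressure (MIP), and, last, "isometric endurance (ISO-M) x1 (press and hold at 50% of the highest MIP". A separate posterior IOPI list has three items: MIP, isometric endurance and isotonic endurance (ISO-T). The section then turns to the Tongueometer, the device participants took home: "To determine lingual exercise, baseline TongueometerTM measurement included anterior ISO-T". That reading feeds the home prescription, which is a fraction of the repetitions achieved at a fraction of maximum pressure.

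The Statistical analysis section says that "differences in baseline measures from pre-treatment to post treatment were calculated" and opens the lingual group with "IOPI measures: average swallow pressure (kPa) over 3 trials". The same group includes "anterior isometric endurance max (seconds), and maximum anterior isotonic endurance (reps". Anterior isotonic endurance is therefore analysed as an IOPI outcome, although the measurement section does not list it as an IOPI measurement.

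**The concern.** Anterior ISO-T is the outcome closest to the trained task, which is repeated anterior presses on the Tongueometer for 8 to 10 weeks. The design has no untreated group, so its pre-to-post change is read directly as a treatment effect. Its meaning depends on the instrument:

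- **IOPI at both visits.** The change is performance on an instrument not used for home training, and the analysis label is right.
- **Tongueometer at both visits.** The change is performance on the training device, and the analysis label is wrong.
- **One device before and the other after.** Any systematic difference between the devices is added in full to the estimated change.

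A reader who follows only the measurement section finds a Tongueometer baseline and no itemised post-treatment anterior ISO-T. That reader could fear the third case.

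**Working it through.** No sample size, power or error-rate figure is at issue, so the check compares the two lists and then the clues around the mismatch.

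**Step 1: match the items.**

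| Outcome analysed under IOPI | In the IOPI lists of Lingual Pressure Measures? |
|---|---|
| Swallow pressure | Yes, anterior |
| Effortful swallow pressure | Yes, anterior |
| Anterior maximum strength | Yes, anterior |
| Anterior isometric endurance | Yes, anterior |
| Anterior isotonic endurance | **No** |
| Posterior maximum strength | Yes, posterior |
| Posterior isometric endurance | Yes, posterior |
| Posterior isotonic endurance | Yes, posterior |

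Analysed: 5 + 3 = 8. Listed: 4 + 3 = 7. There is one mismatch.

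**Step 2: check the units.** The lead-in to the anterior IOPI list allows for repetitions, time or pressure. The two swallow items and MIP give pressures. Isometric endurance gives a time. No listed item gives repetitions. Anterior ISO-T would, and the analysis section gives it in repetitions. The lead-in fits a list of five items better than the four printed.

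**Step 3: check the parallel list.** Isotonic endurance is in the posterior IOPI list, so the IOPI session already included that test. Adding it to the anterior list would make the measurement section agree exactly with the analysis section.

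**Step 4: read the Tongueometer sentence for its purpose.** It explains how the exercise was set. It says the baseline Tongueometer measurement included anterior ISO-T; it does not say that the IOPI version was not taken. Because two manometers were in use at both visits, a reading on the home device to set the exercise and an IOPI reading as an outcome can coexist.

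**Step 5: look for a switch of device.** The Study Visits section says "Post-treatment data were collected at a final study visit" but itemises no lingual test there. The two-weekly repeat of ISO-T under Adherence Monitoring updates the exercise and states neither position nor device. No sentence says or implies that anterior ISO-T was taken on one instrument before treatment and another after.

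**Step 6: size the reach.** Change outcomes in the Statistical analysis section: 1 (EAT-10) + 8 (lingual) + 2 (MBSImP) + 5 (SWAL-QOL) + 12 (ASPEKT) = 28. Anterior ISO-T is one of the 28, and no primary outcome is named among them.

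**The case for a change.** The strongest opposing case is that the documents do not settle the device. The measurement text is continuous prose with no broken table or redaction, and it names ISO-T for the posterior IOPI and, separately, anterior ISO-T for the Tongueometer. The documents never say that the two devices' readings are interchangeable. If different devices had been used, the harm could be material. Take a two-sided one-sample t-test of change at 0.05, no true change, and a device difference of d standard deviations of change. The rejection probability comes from a noncentral t with n − 1 degrees of freedom and noncentrality d√n. At d = 0.25 it is 10.9% for n = 10, 18.6% for n = 20 and 26.3% for n = 30, against a nominal 5%.

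What stands is the inconsistency: the two sections do not agree, and stating the device would help a reader. The error rates do not carry the point further. They require a switch of device that no section describes, and both n and d are assumed because the documents give neither. They show what a shift of arbitrary size does to a t-test and establish nothing particular to this plan. Nor is it right that the documents name only a Tongueometer baseline. That is true of the measurement section, but the analysis section assigns the pre-to-post outcome to the IOPI. Finally, a constant device difference would leave the comparison of the two exercise groups unaffected.

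**Conclusion.** This is a clerical slip, most probably one item missing from the anterior IOPI list, and it calls for no change to the plan. It concerns one of eight lingual outcomes and one of 28 change outcomes. If the IOPI was used at both visits, the analysis is correct as labelled. If the Tongueometer was used at both, the label is wrong, but the variable, the model and the computed result stay the same, although the change would then describe performance on the training device. Only a switch of device between visits would make the change score unsound, and the documents give no sign of one.

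The conclusion rests on two assumptions: that the same device was used before and after treatment, and that the visit records identify it, so that analysts holding the data can name the instrument correctly when they report.

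### Mean pre-to-post change is presented as a treatment effect, but both programmes contain the exercise and nothing in the model separates its effect from other change between visits

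*Combined protocol and SAP*

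**What the plan says.** Study Visits describes the design: "This study used a prospective quasi-experimental design, with pre-test and post-test measures". The first programme is the lingual press task: "Participants were assigned to complete this task 3 times per day". The second keeps that task at a lower daily frequency and adds effortful swallows: "Half of the participants were instructed to complete this task 2 times a day and once a day to do 10 effortful swallows". No untreated, sham or delayed-start group and no repeated baseline is described, and how the halves were formed is not stated.

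The Statistical analysis section opens its inferential part with "To examine treatment effects, differences in baseline measures from pre-treatment to post treatment were calculated" and lists the outcomes. The regression is specified by "Treatment group (Endurance only vs Endurance plus transference) and baseline measures were included as covariates", followed by a reduction step: "Treatment group effects that were not statistically significant were eliminated from the model and re-evaluated". The two categorical outcomes have no group term at all: "Bowker's test of symmetry was used to test for differences in PAS score category and FOIS from pre- to post-treatment". The threshold is 0.05, with sidedness not stated.

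Adherence Monitoring adds weekly virtual contact with a clinician and this retesting: "Every two weeks participants Max MIP x3 and new ISO-T was measured updated number or repetitions, and max press was provided".

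**The concern.** The plan gives a causal name to an uncontrolled quantity. When everyone exercises, the average change is the exercise effect plus everything else that happens to participants between the two visits. Two such sources are plausible from the documents themselves:

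- Maximum press and isotonic repetitions are rehearsed every two weeks, so scores on those tests may rise through familiarity.
- EAT-10 and the SWAL-QOL scores are self-reports from people who know they have completed a programme. No masking of participants is described.

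If either source moves the scores, a significant result could be reported as efficacy although the exercise contributed nothing. At stake is what the trial may claim. The arithmetic of its tests is not in question.

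**Working it through.** **Structure.** The regression is

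change = b0 + b1 × group + b2 × baseline + error.

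- b1 compares two programmes that both contain the exercise.
- b2 adjusts for the starting value.
- Mean change is carried by b0, evaluated at the average baseline. It equals (exercise effect) + (other change common to all). The two parts enter as one sum and no term distinguishes them.
- If group is eliminated, only baseline and the mean change over all participants remain.
- Bowker's test for PAS and FOIS compares pre with post directly, so it has the same limit.

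**Figure to reproduce.** None. The documents give no sample size, power, target effect, SD or pre/post correlation. Everything below except alpha = 0.05 is an assumption.

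**Illustration.** Inputs: exercise effect zero in both groups; shared change δ in baseline SDs; pre/post correlation r; two-sided one-sample t test of mean change.

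- SD of change = √(2 − 2r) baseline SDs. At r = 0.5 this is √1 = 1, so δ is also in SDs of change.
- Noncentrality λ = δ√N / √(2 − 2r). At r = 0.5, N=20 and δ = 0.3, λ = 0.3 × 4.472 = 1.342. At N=40, λ = 0.3 × 6.325 = 1.897.
- Chance of significance = P(T > t*) + P(T < −t*), where T is noncentral t with N − 1 degrees of freedom and noncentrality λ, and t* is the 97.5th percentile of the central t.

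| Shared change (baseline SD), r = 0.5 | N=10 | N=20 | N=40 |
|---|---|---|---|
| 0 | 5.0% | 5.0% | 5.0% |
| 0.1 | 5.9% | 7.1% | 9.5% |
| 0.2 | 8.8% | 13.6% | 23.5% |
| 0.3 | 13.6% | 24.7% | 45.7% |
| 0.5 | 29.3% | 56.5% | 86.9% |

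The rates are per outcome. They rise with N because the shared change is a bias and does not average out.

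**Sensitivity to correlation.** At r = 0.7 the SD of change is √0.6 = 0.775 baseline SDs, so the same shift is easier to detect. A simulated paired t test with δ = 0.3 gave 37.4% at N=20 and 67.5% at N=40.

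**The plan's own procedure.** This was simulated as change on group and centred baseline, with group dropped if p ≥ 0.05 and adjusted mean change then tested (r = 0.7, 8,000 runs per cell, shift in SDs of change).

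| Shift (SD of change), r = 0.7 | N=20 | N=40 |
|---|---|---|
| 0 | 7.0% | 7.3% |
| 0.3 | 29.7% | 52.4% |
| 0.5 | 62.3% | 90.3% |

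The excess over 5% at zero shift is not shared change. The model's standard error treats baseline as fixed and uses a residual variance of 1 − 0.7² = 0.51, whereas the variance of change is 0.60. The pattern otherwise matches the t-test table.

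The group coefficient was significant in 4.5% to 5.4% of runs throughout. That follows by construction, because the same shift was given to both groups.

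**The case against.** The strongest reply is that this is a matter of wording. The design is openly called quasi-experimental. The sentence at issue introduces a calculation, and no explicit rule says that a significant change proves efficacy. The null hypothesis tested is zero mean change. If a shared change exists, rejecting that null is correct, so the rates above are power for change and not type I error in the usual sense. Entry at least 3 months after stroke also limits early spontaneous recovery, and better pressing skill is partly what the programme trains.

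Much of this stands. The tests are valid for change, and only the causal reading fails. But that reading is the one the section gives as its purpose, and no limit on interpretation is attached. The design label supplies none, and the entry window does not address familiarity or expectation.

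Four stronger readings are tempting, and the documents do not support them:

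- *The plan declares false treatment effects well above 5% of the time.* This is conditional. At a shared change of 0.1 SD and N=20 the rate is 7.1%, and at zero it is nominal for a correctly sized test.
- *Several false effects would usually be reported.* Fourteen of the listed outcomes are lingual pressure (8) or self-report (6). At 13.6% each (0.2 SD, N=20, correlation 0.5) and assuming independence, the chance of three or more is about 30%.
- *All eight pressure outcomes are rehearsed.* The two-weekly retests name only maximum press and isotonic repetitions. Isometric endurance, saliva-swallow pressure and effortful-swallow pressure are not listed.
- *The group coefficient is the real treatment effect.* It compares two active programmes with an undescribed allocation. Shared change cancels only if it is equal in both. One programme practises effortful swallows daily with device feedback, and effortful pressure is an outcome, so equality cannot be assumed.

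**Conclusion.** The concern holds as one of interpretation. Mean pre-to-post change in this design does not identify an effect of lingual exercise, and neither covariate can make it do so. That conclusion needs no numerical assumption.

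How often it would mislead cannot be fixed from the documents. With no exercise effect, a correlation of 0.5 and a shared change between 0.1 and 0.5 baseline SD, the chance of significance per outcome runs from about 7% to 57% at N=20 and from about 10% to 87% at N=40. It is 5% if there is no shared change. The documents do not show that shared change of any particular size occurred. The point deserves action because it alters what the trial can claim and the correction is nearly free.

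**What to change.** In the Statistical analysis section:

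1. Replace the purpose clause that opens the pre/post paragraph with *To estimate pre-to-post change*.
2. Report mean change with a 95% CI, and label its Cohen's d *pre-post standardised change*.
3. State that a significant mean change, or a significant Bowker's test for PAS or FOIS, shows that the outcome changed over the 8-10 weeks and does not on its own show that the exercise caused it.
4. For every outcome, report the group coefficient with a 95% CI from the model that includes group, before any elimination, and call it the *between-programme difference*. Do not call it the effect of lingual exercise, and do not interpret it causally unless the allocation method, once described, supports that.

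The cost is wording plus one coefficient per outcome from models already fitted, with no new data or participants. The downside is a less favourable claim: average change is reported as uncontrolled change. Estimating the effect of the exercise itself would need a concurrent group without it, which relabelling cannot supply.
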